Appendix A

10	History of hepatitis B surface antigen or hepatitis C antibody positive (unless associated with documented persistently stable/normal range aspartate aminotransferase [AST] and alanine aminotransferase [ALT] levels), or other clinically active liver disease.	Measured 180 days prior to drug initiation in any diagnosis/procedure position and inpatient or outpatient care setting- Liver disease- ICD-9 diagnosis: 070.xx, 570.xx-573.xx 456.0x-456.2x, 576.8x, 782.4x, 789.5x ICD-9 procedure codes: 39.1x, 42.91	Patorno, [name] et al. "Cardiovascular outcomes associated with canagliflozin versus other non-glipizid antidiabetic drugs: population based cohort study." BMJ 2018;360:k119 http://dx.doi.org/10.1136/bmj.k119 Patorno, [name] et al. "Empagliflozin and the Risk of Heart Failure Hospitalization in Routine Clinical Care: A First Analysis from the Empagliflozin Comparative Effectiveness and Safety (EMPRISE) Study." Circulation . 2019 Apr 8. doi: 10.1161/CIRCULATIONAHA.118.039177
11	Any history of or planned bariatric surgery.	Measured 1825 days prior to drug initiation in any procedure position and inpatient or outpatient care setting- CPT-Code Abbreviation Procedure 43644 -LRYBC-Laparoscopic Roux-en-Y gastric bypass (Roux limb 150 cm or less) 43645 -LRYGBX- Laparoscopic gastric bypass with small intestine reconstruction to limit absorption 43770 -LAGB- Laparoscopic adjustable gastric band 43846 -ORYGB- Open Roux-en-Y gastric bypass (Roux limb 150 cm or less) 43847 -ORYGBX- Open gastric bypass with small intestine reconstruction to limit absorption	Hatoam, Ida J et al. "Clinical Factors Associated With Remission of Obesity-Related Comorbidities After Bariatric Surgery." JAMA Surg . 2016;151(2):130-137. doi:10.1001/jamasurg.2015.3231
12	Estimated glomerular filtration rate (eGFR) <30 ml/min/1.73 m ² at screening (provided by the central laboratory) – For subjects taking metformin: at screening, serum creatinine ≥1.4 mg/dl (124 µmol/l) for men or ≥1.3 mg/dl (115 µmol/l) for women; no contraindication to the use of metformin (including eGFR) based on the label of the country of investigational site	N/A	
13	ALT levels >2.0 times the upper limit of normal (ULN) or total bilirubin >1.5 times the ULN at screening, unless in the opinion of the investigator and as agreed upon by the sponsor's medical officer, the findings are consistent with Gilbert's disease.	N/A	
14	History of malignancy within 5 years before screening (exceptions: squamous and basal cell carcinomas of the skin and carcinoma of the cervix in situ , or a malignancy that in the opinion of the investigator, with concurrence with the sponsor's medical monitor, is considered cured with minimal risk of recurrence).	Measured 1825 days prior to drug initiation in any diagnosis position and inpatient or outpatient care setting- History of malignant neoplasm 140.xx-208.xx (except 173.xx, non-melanoma skin cancer)	Patorno, [name] et al. "Cardiovascular outcomes associated with canagliflozin versus other non-glipizid antidiabetic drugs: population based cohort study." BMJ 2018;360:k119 http://dx.doi.org/10.1136/bmj.k119 Patorno, [name] et al. "Empagliflozin and the Risk of Heart Failure Hospitalization in Routine Clinical Care: A First Analysis from the Empagliflozin Comparative Effectiveness and Safety (EMPRISE) Study." Circulation . 2019 Apr 8. doi: 10.1161/CIRCULATIONAHA.118.039177
15	History of human immunodeficiency virus (HIV) antibody positive.	Measured 1825 days prior to drug initiation in any diagnosis position and inpatient or outpatient care setting- 042 Human immunodeficiency virus [HIV] disease 079 53 Human immunodeficiency virus, type 2 [HIV-2] V08 Asymptomatic human immunodeficiency virus [HIV] infection status OR filled prescription for HIV treatment: (Please see HIV Treatment sheet)	Patorno, [name] et al. "Cardiovascular outcomes associated with canagliflozin versus other non-glipizid antidiabetic drugs: population based cohort study." BMJ 2018;360:k119 http://dx.doi.org/10.1136/bmj.k119 Patorno, [name] et al. "Empagliflozin and the Risk of Heart Failure Hospitalization in Routine Clinical Care: A First Analysis from the Empagliflozin Comparative Effectiveness and Safety (EMPRISE) Study." Circulation . 2019 Apr 8. doi: 10.1161/CIRCULATIONAHA.118.039177
16	Subject has a current clinically important hematological disorder (e.g., symptomatic anemia, proliferative bone marrow disorder, thrombocytopenia).	Measured 180 days prior to drug initiation in any diagnosis position and inpatient or outpatient care setting- ICD-9 Diagnosis Codes: 238.4x, 289.83, 238.71, 280.x-285.x, 287.3x, 287.4x, 287.5x	Expert in this study area advised on the codes used for this inclusion/exclusion criteria.
17	Investigator's assessment that the subject's life expectancy is less than 1 year, or any condition that in the opinion of the investigator would make participation not in the best interest of the subject, or could prevent, limit, or confound the protocol-specified safety or efficacy assessments.	Measured 180 days prior to drug initiation- CCI >=10	Gagne, Josh J et al. "A combined comorbidity score predicted mortality in elderly patients better than existing scores." J Clin Epidemiol . 2011 Jul;64(7):749-59. doi: 10.1016/j.jclinepi.2010.10.004. Sun, Jenny W et al. "Validation of the Combined Comorbidity Index of Charlson and Elixhauser to Predict 30-Day Mortality Across ICD-9 and ICD-10." Med Care . 2018 Sep;56(9):812. doi: 10.1097/MLR.0000000000000954.
18	Major surgery (i.e., requiring general anesthesia) within 3 months of the screening visit or any surgery planned during the subject's expected participation in the study (except minor surgery; i.e., outpatient surgery under local anesthesia).	Measured 90 days prior to drug initiation in any diagnosis position and inpatient or outpatient care setting- Major surgery selected from codes range 35.x-84.x	
19	Any condition that, in the opinion of the investigator, would compromise the well-being of the subject or prevent the subject from meeting or performing study requirements.	N/A	
20	Current use of other sodium glucose co-transporter 2 (SGLT2) inhibitor.	Measured 180 days prior to drug initiation as a dispensing of one of the following drugs- empagliflozin, dapagliflozin, ertugliflozin	
21	Known allergies, hypersensitivity, or intolerance to canagliflozin or its excipients.	N/A	
22	Current use of a corticosteroid medication or immunosuppressive agent, or likely to require treatment with a corticosteroid medication (for longer than 2 weeks in duration) or an immunosuppressive agent. Note: subjects using inhaled, intranasal, intra-articular, or topical corticosteroids, or corticosteroids in therapeutic replacement doses may participate.	Measured 180 days prior to drug initiation as a dispensing of one of the following drugs- Systemic corticosteroids (With Route of Administration is intravenous)- Cortisone, hydrocortisone, prednisone, prednisolone, methylprednisolone, triamcinolone, dexamethasone, betamethasone. immunosuppressive agents o RA, AS, and PsA: methotrexate, hydroxychloroquine, azathioprine, cyclosporine, leflunomide, minocycline, sulfasalazine. o SLE: hydroxychloroquine, azathioprine, mycophenolate mofetil. o IBD: azathioprine, mercaptopurine	Patorno, [name] et al. "Cardiovascular outcomes associated with canagliflozin versus other non-glipizid antidiabetic drugs: population based cohort study." BMJ 2018;360:k119 http://dx.doi.org/10.1136/bmj.k119 Patorno, [name] et al. "Empagliflozin and the Risk of Heart Failure Hospitalization in Routine Clinical Care: A First Analysis from the Empagliflozin Comparative Effectiveness and Safety (EMPRISE) Study." Circulation . 2019 Apr 8. doi: 10.1161/CIRCULATIONAHA.118.039177 Desai, Rishi et al. "Risk of serious infections associated with use of immunosuppressive agents in pregnant women with autoimmune inflammatory conditions: cohort study" BMJ 2017; 356 doi: https://doi.org/10.1136/bmj.j895
23	Received an active investigational drug (including vaccines) or used an investigational medical device within 3 months before Day 1/baseline or received at least one dose of canagliflozin in a prior study.	Already applied based on the canagliflozin and comparator washout, but measured again 90 days prior to drug initiation as a dispensing for canagliflozin	

Appendix A

24	History of drug or alcohol abuse within 3 years before screening.	
Measured 1095 days prior to drug initiation in any diagnosis position and inpatient or outpatient care setting- Alcohol abuse or dependence 291.xx, 303.xx, 305.0x, 571.0x, 571.1x, 571.2x, 571.3x, 357.5x, 425.5x, E860.0x, V11.3x Drug abuse or dependence 292.xx, 304.xx, 305.2x-305.9x, 648.3x
 
Patorno, [name] et al. "Cardiovascular outcomes associated with canagliflozin versus other non-gliflozin antidiabetic drugs: population based cohort study." BMJ 2018;360:k119 http://dx.doi.org/10.1136/bmj.k119
 
Patorno, [name] et al. "Empagliflozin and the Risk of Heart Failure Hospitalization in Routine Clinical Care: A First Analysis from the Empagliflozin Comparative Effectiveness and Safety (EMPRISE) Study." Circulation. 2019 Apr 8. doi: 10.1161/CIRCULATIONAHA.118.039177

25	Pregnant or breastfeeding or planning to become pregnant or breastfeed during the study.	
26	Employees of the investigator or study center, with direct involvement in the proposed study or other studies under the direction of that investigator or study center, as well as family members of the employees or the investigator.	N/A

Appendix A

Trial ID	sNDA22
Trial Name (with web links)	CANVAS
NCT	NCT01032629
Trial category	Secondary indication
Therapeutic Area	Endocrinology
RCT Category	4a- Unintended S with label change
Brand Name	Invokana
Generic Name	Canagliflozin
Sponsor	Janssen Research & Development, LLC
Year	2017
Measurable endpoint	Major Adverse Cardiovascular Events, Including CV Death, Nonfatal Myocardial Infarction (MI), and Nonfatal Stroke
Exposure	Canagliflozin
Comparator	Placebo
Population	50% on insulin, 47% using Sulfonylurea, 73% Metformin, 72% statin
Trial finding	HR = 0.86 (95% CI 0.75–0.97)
No. of Patients	4330
Non-inferiority margin	HR = 1.3
Assay Sens. Endpoint	
Assay Sens. Finding	
Power	0.90. With 688 cardiovascular safety events recorded across the trials, there would be at least 90% power, at an alpha level of 0.05, to exclude an upper margin of the 95% confidence interval for the hazard ratio of 1.3.
Blinding	
Statistical Method	Cardiovascular safety was to be shown if the upper boundary of the 95% confidence interval of the hazard ratio with canagliflozin as compared with placebo was less than 1.3, and superiority was to be shown if the upper boundary was less than 1.0.

Appendix A

Mortality- Dependent on data source.

1. All-cause mortality / inpatient mortality

Identified using the vital status file-

Medicare

Identified using the discharge status codes-

Optum-

- 20 = EXPIRED
- 21 = EXPIRED TO BE DEFINED AT STATE LEVEL
- 22 = EXPIRED TO BE DEFINED AT STATE LEVEL
- 23 = EXPIRED TO BE DEFINED AT STATE LEVEL
- 24 = EXPIRED TO BE DEFINED AT STATE LEVEL
- 25 = EXPIRED TO BE DEFINED AT STATE LEVEL
- 26 = EXPIRED TO BE DEFINED AT STATE LEVEL
- 27 = EXPIRED TO BE DEFINED AT STATE LEVEL
- 28 = EXPIRED TO BE DEFINED AT STATE LEVEL
- 29 = EXPIRED TO BE DEFINED AT STATE LEVEL
- 40 = EXPIRED AT HOME (HOSPICE)
- 41 = EXPIRED IN A MEDICAL FACILITY (HOSPICE)
- 42 = EXPIRED - PLACE UNKNOWN (HOSPICE)

Truven-

- 20 - Died
- 22 - Died
- 23 - Died
- 24 - Died
- 25 - Died
- 26 - Died
- 27 - Died
- 28 - Died
- 29 - Died
- 40 - Other died status or Expired at home (Hospice claims only) (depends on year)

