6.3.1 Outcome variables

Effectiveness outcomes of interest (definitions provided in **Appendix A**):

- **Primary outcome:** 3-point major adverse cardiovascular events (MACE), i.e., non-fatal myocardial infarction, non-fatal stroke, or CV mortality
- Secondary outcomes: Individual components:
 - Hospital admission for MI (for purposes of this individual component, fatal MI is included)
 - Hospital admission for stroke (for purposes of this individual component, fatal stroke is included)
 - All-cause mortality/CV mortality:
 - All-cause inpatient mortality identified using discharge status codes will be used as a proxy for “CV mortality” in commercial databases
 - Information on CV mortality through data linkage with the National Death Index (NDI) will only become available at a later date for Medicare and will be used in secondary analyses.

Control outcomes of interest (control outcomes only serve to assess aspects of study validity but are not further interpreted):

1. Diabetes Ketoacidosis (we expect to see a positive association; Neal et al., 2017)
2. Heart failure (we expect to see a protective effect; Neal et al., 2017)

Control outcome definitions

Outcome	Definition	Comments
Control Outcomes		
Diabetic Ketoacidosis	Inpatient ICD-9 diagnosis: 250.1x	Note- The corresponding ICD-10 codes will also be used
Heart Failure	Inpatient ICD-9 diagnosis (primary diagnosis): 428.x, 398.91, 402.01, 402.11, 402.91, 404.01, 404.11, 404.91, 404.03, 404.13, 404.93	Note- The corresponding ICD-10 codes will also be used

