	Major Adverse Cardiovascular Events, Including CV Death, Nonfatal Myocardial Infarction (MI), and Nonfatal Stroke HR = 0.86 (95% CI 0.75-0.97)	
Measured 1 day after drug initiation in diagnosis position specified below and inpatient care setting: Inpatient mortality/MI/Stroke --
 
For MI Any diagnosis position in inpatient care setting ICD-9 Dx 410.X (acute myocardial infarction) excluding 410.x2 (subsequent episode of care)
 
For stroke Primary diagnosis position in inpatient care setting ICD-9 discharge diagnosis: 430.xx Subarachnoid hemorrhage (SAH) 431.xx Intracerebral hemorrhage (ICH) 433.x1 Occlusion and stenosis of precerbral arteries with cerebral infarction 434.xx (excluding 434.x0) Occlusion and stenosis of cerebral arteries with cerebral infarction 436.x Acute, but ill-defined cerebrovascular events
 
Mortality- See Mortality Sheet.
	
For MI: →PPV 94% in Medicare claims data [Kiyota Y, Schneeweiss S, Glynn RJ, Cannuscio CC, Avorn J, Solomon DH. Accuracy of Medicare claims-based diagnosis of acute myocardial infarction: estimating positive predictive value on the basis of review of hospital records. American heart journal 2004;148:99-104.] →PPV 88.4% in commercially-insured population [Wahl PM, Rodgers K, Schneeweiss S, et al. Validation of claims-based diagnostic and procedure codes for cardiovascular and gastrointestinal serious adverse events in a commercially-insured population. Pharmacoepidemiology and Drug Safety 2010;19:596-603.]
 
For stroke: PPV 0.85% or higher for ischemic stroke PPV ranging from 80% to 98% for hemorrhagic stroke →[Andrade SE, Harrold LR, Tjia J, et al. A systematic review of validated methods for identifying cerebrovascular accident or transient ischemic attack using administrative data. Pharmacoepidemiology and Drug Safety 2012;21 Suppl 1:100-28.] →[Tirschwell DL, Longstreth WT, Jr. Validating administrative data in stroke research. Stroke: a journal of cerebral circulation 2002;33:2465-70.] →[Roumie CL, Mitchel E, Gideon PS, Varas-Lorenzo C, Castellsague J, Griffin MR. Validation of ICD-9 codes with a high positive predictive value for incident strokes resulting in hospitalization using Medicaid health data. Pharmacoepidemiology and drug safety 2008;17:20-6.]
	Can't be measured in claims but not important for the analysis
	INCLUSION CRITERIA			

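### The death component of the pooled primary MACE is defined differently in Medicare and in the commercial databases, and deaths could account for much of an apparent replication

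*Combined protocol and SAP*

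**What the plan says.** Three places define the death component.

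- **Appendix A, primary outcome row.** The composite is labelled "Inpatient mortality/MI/Stroke" with no exception by database. The row then passes the detail on: "Mortality- See Mortality Sheet".
- **Appendix A, Mortality sheet.** It opens "Mortality- Dependent on data source". Under a heading that names both all-cause and inpatient mortality, Medicare deaths are "Identified using the vital status file". Optum and Truven (taken here as MarketScan) deaths are "Identified using the discharge status codes": codes 20-29 and 40-42, the last three being hospice codes that include death at home.
- **Section 6.3.1.** "All-cause inpatient mortality identified using discharge status codes will be used as a proxy for" CV mortality, and this is limited to the commercial databases. CV death through the National Death Index (NDI) "will only become available at a later date for Medicare and will be used in secondary analyses".

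Section 10 foresees a pooled analysis of all three databases. MI, stroke and mortality are separate secondary outcomes in Section 6.3.1, and Section 14.1 asks for results by endpoint. The plan specifies no MI/stroke composite without death, no common death definition and no comparison of HRs across databases. Section 13 shows no report name or run date.

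**The concern.** Two programmers could code different Medicare endpoints from this text. One would follow the outcome row and count only inpatient deaths. The other would follow the Mortality sheet and count every death in the vital status file. The second reading is the more natural one. Under it, the database with most of the events uses a wider death definition than the other two, and no database measures the CV death that the trial counted.

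The choice matters because deaths are a sizeable part of the expected events and are already unequal between the matched arms. A pooled HR near the trial's 0.86 would be read as replication of a cardiovascular effect. If much of it came from all-cause deaths over a median follow-up of four to five months, that reading would need support from MI and stroke.

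**Working it through.** **Inputs.** Section 10, canagliflozin vs DPP4i: 76,101 matched patients per arm pooled (19,532 Optum, 23,168 MarketScan, 33,401 Medicare), pooled risk 12.65 per 1,000, target HR 0.86, two-sided alpha 0.05. Section 9: risks of 7.58, 7.81 and 22.56 per 1,000. Section 9 censoring table: 374 referent and 215 exposed deaths, 589 in all.

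**1. The plan's own figure.** Events = 2 × 76,101 × 12.65/1,000 = 1,925.4. Power = Φ(|ln 0.86| × √1,925.4/2 − 1.96) = Φ(1.349) = 0.911, which matches the stated 0.9113.

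**2. Event base and Medicare share.** The pooled 12.65 is the simple mean (7.58 + 7.81 + 22.56)/3. Weighting by matched patients gives 296.1 + 361.9 + 1,507.1 = 2,165.0 events. Both bases are carried below. Medicare share: 1,507.1/2,165.0 = 0.70.

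**3. Deaths.** Ratio 215/374 = 0.57. SE of the log ratio = √(1/215 + 1/374) = 0.086, so the approximate 95% CI is 0.49-0.68. Deaths equal 589/2,165 = 27% to 589/1,925 = 31% of expected events.

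**4. Limiting case: no MI/stroke effect and every death a first event.** The non-death events are split equally.
- 1,925 base: (1,925.4 − 589)/2 = 668.2 per arm; (668.2 + 215)/(668.2 + 374) = 0.847.
- 2,165 base: 788.0 per arm; (788.0 + 215)/(788.0 + 374) = 0.863.

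**5. Overlap.** The censoring table comes from the dummy-outcome run, in which follow-up did not stop at MI or stroke. Some deaths may therefore follow an event already counted. Let f be that share (assumed), with total first events held fixed:

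| f | 1,925 base | 2,165 base |
|---|---|---|
| 0 | 0.847 | 0.863 |
| 10% | 0.862 | 0.876 |
| 25% | 0.883 | 0.896 |
| 50% | 0.921 | 0.929 |

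Example, 25% on the 1,925 base: first-event deaths 280.5 and 161.25, other events 741.8 per arm, (741.8 + 161.25)/(741.8 + 280.5) = 0.883. On that base the ratio stays at or below 0.86 only if f is at most about 9%. On the larger base it does not go below 0.863. Approximate 95% upper bounds are 0.97 at 25% overlap and 1.01 at 50%.

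**6. A narrower death definition.** This is a different question: MI/stroke events stay as they are and some deaths drop out. If half of all deaths dropped out (assumed, same split), the ratios become (668.2 + 107.5)/(668.2 + 187) = 0.907 and (788.0 + 107.5)/(788.0 + 187) = 0.918.

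**7. Person-time.** The by-arm median follow-up ratios run from 142/153 = 0.93 to 134/121 = 1.11. Used as a rough person-time range, they spread the no-overlap result to 0.82-0.88.

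**8. Power without deaths.** Removing all 589 from the 1,925 base leaves 1,336.4 events: Φ(0.1508 × √1,336.4/2 − 1.96) = Φ(0.797) = 0.79. On the 2,165 base it is 0.85.

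The sulfonylurea comparison shows the same pattern: 364 vs 184 deaths, and a no-overlap ratio of 0.845-0.858.

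**The case against.** The difference by data source is disclosed. The outcome row defers to the Mortality sheet, and Section 6.3.1 agrees with that sheet, so the inpatient label can be read as loose wording. That stands as the likeliest reading. It leaves the label to be corrected and the endpoint still different across databases.

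MI, stroke and mortality are already reported separately, so a result driven by deaths would be visible. This stands in large part. What is missing is the combined MI/stroke estimate to set beside the primary HR.

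A reader might infer that the 374 to 215 split is produced by the Medicare file, or by mixing definitions. The documents do not support this, because deaths are not given by database. A reader might also infer residual frailty. Measured frailty, comorbidity score and hospitalisation are balanced after matching, with standardised differences of about 0.00-0.01. On the other side, laboratory values were left out of the propensity score, and matched creatinine differs by 0.14 SD among those with a value. Neither fact settles whether the imbalance is confounding or a real effect.

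That Medicare deaths are counted in any setting is itself an inference, from the all-cause heading and the absence of an inpatient limit. Finally, imposing discharge-status death on the Medicare primary would discard deaths outside hospital. That trade-off is contestable, so the common definition belongs in a sensitivity analysis.

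**Conclusion.** The inconsistency is real and should be resolved before the comparative analysis. The pooled primary combines vital-status death in the database with about 70% of expected events and discharge-status death, hospice codes included, in the other two. Neither is CV death.

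On the plan's own counts, deaths could account for much of an apparent replication: a composite ratio of about 0.85-0.86 with no overlap, and about 0.88-0.93 with 25-50% overlap, when MI and stroke do not differ.

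A reader might infer that deaths alone would yield 0.86. That is a limiting case, not a forecast: it needs an exactly null MI/stroke effect and almost no death after a counted event.

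The figures also assume roughly equal person-time and that the expected events include these deaths. They combine risks from an April 2019 report with deaths from the November 2019 match. They do not show where the imbalance comes from.

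**What to change.** Reconcile Section 6.3.1, the Appendix A primary outcome row and the Mortality sheet, so that the death definition for the primary endpoint is explicit for each database, including whether Medicare vital-status deaths count in any setting. Before Section 13 is run, pre-specify alongside the primary HR:

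- (a) an MI/stroke composite without death;
- (b) HRs for each database, with deaths by arm and database;
- (c) a sensitivity analysis with one discharge-status death definition in all three databases, treating hospice codes 40-42 the same way in each. This assumes that Medicare inpatient claims carry a discharge status.

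Keep NDI CV death as the planned Medicare secondary analysis.

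The cost is protocol wording and a little more analysis. The MI/stroke composite is less precise: superiority power is about 0.79 on the 1,925-event base if all 589 deaths are removed, and higher if some of those deaths follow a counted event.
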